5.5. Safety analyses

All endpoints listed above will be summarized by study visit and cohort as described in section 5.1. There are no formal hypothesis tests for safety.

The number and percentage of eyes reaching BCDVA 20/40 or better, and worse than 20/40 at each visit will be prepared.

Rates for adverse events specified in ISO 11979-7:2014 Annex B for posterior chamber IOLs will be summarized at each visit.

Rates of device-related SSIs and device deficiencies will be summarized as described in 5.1 above.

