8.3.1 SAFETY OUTCOMES

8.3.1.1 ADVERSE EVENTS AND DEVICE DEFICIENCIES

Adverse events and device deficiencies will be summarized at each study visit based on the safety population. The number and percentage of eyes reported with the 3-month cumulative and persistent adverse events will be calculated. [REDACTED]

[REDACTED]

[REDACTED]

[REDACTED]

[REDACTED]

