1 TITLE PAGE

Protocol Number:	ClarVista CP-00004 / NCT03050697
Medical Specialty:	Surgical
Project Name /Number:	NA
Sponsor Name & Address:	CLARVISTA MEDICAL, INCORPORATED [name] [name] [contact] [contact]
Test Article(s) / Product(s):	ClarVista HARMONT® Modular Toric Intraocular Lens System

SAP CP-00004

ClarVista Medical, Inc.

Statistical Analysis Plan for Protocol CP-00004

A Prospective, Multi-Center Study to Evaluate the Safety and Performance of the ClarVista HARMONI® Modular Toric Intraocular Lens System for the Treatment of Pre-Existing Corneal Astigmatism and Aphakia Following Cataract Surgery

Sponsor

ClarVista Medical, Incorporated
[name]
[name]
[contact]
[contact]

Original Version Date

29 June 2017

SAP CP-00004

ClarVista Medical, Inc.

Table of Contents

1. Purpose	3
2. Scope	3
3. Software	3
4. Design and Objectives	3
5. Statistical Analyses	3
6. Sample Size	6
7. Analysis Populations	7
█ [REDACTED]	
█ [REDACTED]	
10. Interim Analyses	8
11. Deviations from the Statistical Analysis Plan	8
12. References	8

SAP CP-00004

ClarVista Medical, Inc.

1. Purpose

This Statistical Analysis Plan documents and describes the planned analyses for study CP-00004. This is a study to evaluate the safety and performance of the HARMONI Modular Toric Intraocular Lens System (HMTIOL) in patients with pre-existing corneal astigmatism. Specifically, the intent is

- To evaluate the refractive outcomes including astigmatism correction with HMTIOL in primary cataract surgery
- To evaluate axial and rotational stability of the HMTIOL

Given these goals, there are no formal hypothesis tests for safety or effectiveness. All results will be purely descriptive.

2. Scope

This document is based on the Investigational Plan CP-00004. [REDACTED]

As the multi-center study described in the Investigational Plan was not actually implemented, analyses described here supersede those described in the Investigational Plan.

3. Software

Statistical analyses will be performed with SAS System Software version 9.4 or above (SAS Institute, Cary, N.C.), R version 3.3 or above (R Core Team, <http://www.R-project.org>), or other validated statistical software package.

4. Design and Objectives

CP-00004 was designed as a prospective, multi-center, cohort study. However only one center actually enrolled patients in the trial.

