5.4. Safety Endpoints

- Preservation of BCDVA
- Adverse Events as outlined in ISO 11979-7:2014 Annex B
- Rate of device-related Secondary Surgical Interventions (SSIs) other than optic exchange or rotational adjustment of the HMTIOL
- Device deficiencies

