7.1.1. SAFETY POPULATION

The Safety Population includes eyes with attempted study lens implantation, (successful or aborted after contact with the eye). The intraoperative and postoperative AEs and DDs will be summarized based on the safety population.

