7.1.3. PER PROTOCOL POPULATION

The Per Protocol (PP) Population contains eyes with successful HMTIOL implantations during surgeries and do not have a major protocol deviation (such as improperly enrolled in the study or lens power calculation errors) and will be considered the primary population for the analysis of performance outcomes. The performance outcomes (UCDVA, BCDVA, and prediction error) will also be evaluated based on the per protocol population.

The protocol deviations will be categorized prior to the analysis.

[REDACTED]

SAP CP-00004

ClarVista Medical, Inc.

8. Interim Analyses

[figure not shown]
There are no plans for formal interim analyses for the purposes of study modification or possible early termination. Any interim analyses will be administrative in nature and results will not be distributed to Investigators or subjects to prevent bias from exposure to accruing study results.

9. Deviations from the Statistical Analysis Plan

Any deviations from the Statistical Analysis Plan will be noted and described with appropriate statistical and clinical rationale as needed. Discrepancies from the Investigational Plan are noted and due primarily to the study design modification from a multi-center to single center trial, without the corresponding amendment to the protocol.

10. References

1. ISO 11979-7:2014 Ophthalmic implants — Intraocular lenses — Part 7: Clinical investigations.
2. Note to File Re: Correction to Appendix A – Table 1: Schedule of Assessments_June 26, 2017

Alcon - Business Use Only

Document: TDOC-0055990

Status: Effective

Effective Date: 24-Apr-2019

Version: 1.0; CURRENT; Most-Recent; Effective

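### The readable SAP does not carry over the protocol's 3-month cumulative and persistent AE rates, and SAP 5.5 and 7.1.1 are not reconciled on which AEs are summarized and how

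*SAP*

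**What the plan says.** **Protocol.** Section 7.1 lists AE rates among the safety outcomes and does not tie them to an external list. Section 6.1.1 defines an AE broadly and includes adverse device effects. Section 8.3.1.1 plans two things. One is a by-visit summary: "Adverse events and device deficiencies will be summarized at each study visit based on the safety population". The other is a whole-study summary: "The number and percentage of eyes reported with the 3-month cumulative and persistent adverse events will be calculated". The planned analyses in the synopsis also call for cumulative and persistent AEs at 3 months.

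**SAP.** Section 2 (Scope) settles precedence: "analyses described here supersede those described in the Investigational Plan". Section 5.4 names the AE endpoint as "Adverse Events as outlined in ISO 11979-7:2014 Annex B". Section 5.5 gives a general rule, "All endpoints listed above will be summarized by study visit and cohort as described in section 5.1", and then a specific one for AEs: "Rates for adverse events specified in ISO 11979-7:2014 Annex B for posterior chamber IOLs will be summarized at each visit". Section 7.1.1 adds "The intraoperative and postoperative AEs and DDs will be summarized based on the safety population", with no ISO limit, time frame or counting rule. The section on deviations from the SAP says: "Discrepancies from the Investigational Plan are noted and due primarily to the study design modification from a multi-center to single center trial".

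Neither cumulative nor persistent AE rates are mentioned anywhere in the readable SAP.

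**The concern.** The protocol's AE analysis has a by-visit part and a 3-month part. The SAP's safety section keeps the by-visit part, words it around an ISO annex, and is silent on the 3-month part. Because the SAP overrides the protocol's analyses, the protocol sentence cannot be relied on to fill the gap.

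The study is descriptive and tests no hypotheses, so its tables are its safety result. A reader will want to know how many eyes had an AE by 3 months and how many still had one then. A set of by-visit percentages does not answer the first question. It answers the second only if the table counts events present at the visit, which the SAP does not say. Events outside the annex have no specified rate, only the unformatted summary in 7.1.1.

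The SAP's general explanation for differences from the protocol is the move from several centers to one. That move has no bearing on whether an eye can be counted once over 3 months.

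**Working it through.** Neither document states an AE rate, so there is no planned figure to reproduce. The check is a comparison of the texts, followed by a bound on what by-visit rates can tell.

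**Step 1: compare the texts.**

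| Element | Protocol 7.1, 8.3.1.1 | SAP 5.4, 5.5 | SAP 7.1.1 |
|---|---|---|---|
| Which AEs | All AEs | ISO annex events | AEs, no list named |
| By-visit summary | Yes | Yes | Not stated |
| Cumulative to 3 months | Yes, eyes and % | Not stated | Not stated |
| Persistent at 3 months | Yes, eyes and % | Not stated | Not stated |
| Population | Safety Population | Not stated | Safety Population |

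The sentence in SAP 7.1.1 also stands in Protocol 8.2.1. There it names the population, and 8.3.1.1 supplies the calculation. The SAP carried over the population sentence but has no readable counterpart to the 3-month calculation.

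**Step 2: what by-visit rates determine.** Inputs:
- n = 17 eyes (SAP section 6)
- k = 4 post-operative visits: 1 Day, 1 Week, 1 Month and 3 Months (SAP section 4)
- e = eyes affected at each visit (assumed, for illustration)

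With all eyes observed at every visit, the share of eyes ever affected satisfies

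e/n ≤ cumulative share ≤ min(n, k × e)/n.

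The lower bound is the same eyes each time; the upper bound is different eyes each time.

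- e = 1, k = 4: each visit shows 1/17 = 5.9%. The cumulative share lies between 1/17 = 5.9% and 4/17 = 23.5%.
- e = 2, k = 4: each visit shows 2/17 = 11.8%. The range is 2/17 = 11.8% to 8/17 = 47.1%.
- e = 1, with the day of surgery as a fifth time point: the upper end becomes 5/17 = 29.4%.

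The same by-visit table is therefore compatible with very different cumulative results.

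**Step 3: persistence.** Take one eye with an event that starts at 1 Week and is still present at 3 Months. If the by-visit table counts onsets, the 3-month row shows 0/17. If it counts events present at the visit, the row shows 1/17 = 5.9%. The SAP does not say which applies, so the 3-month row can stand in for the persistent rate only under the second reading, and then only for listed events.

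**The case against.** The strongest reply is that the SAP has not removed anything outright.

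- **SAP 7.1.1.** It commits to summarizing intraoperative and postoperative AEs with no ISO restriction. A reader might infer from 5.5 that only ISO-listed events will be reported, and only by visit. The documents do not support that, because the 7.1.1 summary could cover all AEs over the whole study. This stands. What remains is that 7.1.1 gives no rate, time frame, once-per-eye rule or persistence rule, and does not say how it relates to 5.5.
- **The ISO annex.** Its content is not in the documents. Which events it omits, and whether its rates are cumulative or persistent by definition, cannot be checked. This also stands. Even so, the SAP text specifies a by-visit format and should state any other format it intends.
- **Text that cannot be seen.** SAP numbering runs from 5.5 to 5.7, two entries between 7 and 10 in the contents list are redacted, and a redacted block follows 7.1.3. So it cannot be said that the study will never report the share of eyes affected. The AE sentence in 5.5, however, is complete as printed.
- **The 3-month visit row.** It may partly show eyes still affected, as step 3 of the working sets out. This is conceded.
- **Size.** The ratio of 4/17 to 1/17 might be read as a fourfold understatement. It is only the extreme allocation; with the same eye each time there is no understatement.
- **Consequence.** This is a small single-center feasibility study, all AEs are reviewed weekly (Protocol 6.4), and serious and device-related events are expedited (Protocol 6.3.1). Those are safeguards during conduct and do not replace a reported rate. They do show that nothing is lost beyond recovery.

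**Conclusion.** The point holds in a limited form. The readable SAP overrides the protocol's analyses and does not specify the 3-month cumulative and persistent AE rates that the protocol planned. SAP 5.5 and 7.1.1 leave open which AEs are summarized and in what format. The general reason given for differences from the protocol does not explain this one.

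The size cannot be stated as a bias, because the documents contain no AE rate. The range of 5.9% to 23.5% shows how little one affected eye per visit reveals about the cumulative share. It rests on 17 eyes all observed at four visits and on an assumed event count.

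Since the SAP was written knowing that one center had enrolled and that 17 eyes had been treated, a reader might infer that safety reporting was narrowed in light of results. Nothing in the documents shows this; an omission in redrafting fits the text equally well.

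The change is worth making because it restores an analysis that the sponsor itself planned. It does not call the conduct of the study into question.

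**What to change.** In SAP 5.5, restore the protocol rule and link it to 7.1.1:

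- For Safety Population eyes, report the number and percentage with each ocular AE, and with any ocular AE, cumulatively through 3 months. Count each eye once per row and do not limit the table to the ISO list.
- For the same eyes, report the number and percentage with AEs persistent at 3 months, and define persistent.
- Report non-ocular AEs per subject. Protocol 6.2.1.1 allows serious events to be non-ocular and one or both eyes may be enrolled, so an eye denominator does not suit them.
- Keep the ISO by-visit table as an additional table, and say whether it counts onsets or events present at the visit.
- Subsets for serious and device-related AEs are optional; the readable text of 8.3.1.1 does not call for them.

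If the cumulative and persistent rates are left out on purpose, the SAP should give the reason in its section on deviations.

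The cost is a few sentences in the SAP and one or two extra tables. The AE assessments in Protocol 6.2.1 already record diagnosis, seriousness, relationship and outcome, including whether an event is ongoing, so no new data are needed.

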5.7. Effectiveness Endpoints

Performance Outcomes:

1. Post op MRCYL for eyes implanted with HMTIOL at 1 and 3 months
2. Post op MRCYL prediction error for eyes implanted with HMTIOL at 1 and 3 months
3. Post op SEQ Prediction Error at 1 and 3 months
4. UCDVA by study visit
5. BCDVA by study visit

SAP CP-00004

ClarVista Medical, Inc.

- 6. IOL meridian misalignment on the day of surgery
- 7. Rotation of IOL meridian from the day of surgery to 3 months, and between all adjacent visits
 - a. Meridian rotation $\leq 5^\circ$
 - b. Meridian rotation $< 10^\circ$
 - c. Meridian rotation $< 20^\circ$
 - d. Meridian rotation $< 30^\circ$
 - e. Absolute value of rotation
- 8. Reduction in cylinder power of eye implanted with HMTIOL (in Diopters) at 3 months
 - a. Absolute preop magnitude of K (or total corneal cylinder) minus the absolute post op magnitude of MRCYL at the corneal plane
- 9. Percentage reduction in cylindrical power of eye implanted with HMTIOL at 3 months
 - a. Absolute preop magnitude of K (or total corneal cylinder) minus the absolute post op magnitude of MRCYL at the corneal plane expressed as a percentage of the absolute preop magnitude of K (or total corneal cylinder)

5.8. Effectiveness Analyses

All endpoints listed above will be summarized by study visit and cohort as described in section 5.1 based on the Implanted Eye Population.

5.8.1. BCDVA

the number and percentage of eyes reaching BCDVA 20/20 or better, 20/25 or better, 20/32 or better, 20/40 or better, and worse than 20/40 at each visit will be prepared.

5.8.2. UCDVA

The proportion of eyes with UCDVA of 20/20 or better, 20/25 or better, 20/32 or better, 20/40 or better, and worse than 20/40 at each visit will be summarized at the preoperative and every postoperative visit.

5.8.3. PREDICTION ERROR (PE)

MRSE prediction error will be calculated at 3 months for each implanted eye as follows:

MRSE PE = Postoperative MRSE adjusted to 6 meters – MRSE TRRE (target residual refractive error)

MRCYL prediction error will be calculated at 3 months for eyes implanted with HMTIOL as follows:

MRCYL PE = Postoperative MRCYL adjusted to 6 meters – MRCYL TRRE (target residual refractive error)

Descriptive statistics for continuous outcomes will be provided for MRSE PE and MRCYL PE at each visit based on Implanted-eye Population. Additionally, the number and percentage of eyes with a PE within ± 0.50 D of target and of ± 1.00 D of target will be derived for each postoperative visit.

SAP CP-00004

ClarVista Medical, Inc.

5.8.4. MISALIGNMENT OF IOL MERIDIAN

The final rotational meridian of the IOL will be compared to the planned position. The absolute value of rotation will be described by mean, median, and maximum values. The signed value of rotation will be described by mean, SD, minimum and maximum values. The number and percentage of eyes with deviation $\leq 5^\circ$, $< 10^\circ$, $< 20^\circ$, and $< 30^\circ$ from the planned meridian will be calculated.

5.8.5. ROTATION OF IOL MERIDIAN

The rotation of IOL meridian will be calculated for each eye from Day 0 to every postoperative visit. Descriptive statistics for continuous variables will be used to summarize the rotation angle at each visit. The absolute value of rotation will be described by mean, median, and maximum values. [REDACTED] The number and percentage of eyes with rotation $\leq 5^\circ$, $< 10^\circ$, $< 20^\circ$, and $< 30^\circ$ will be calculated at each visit.

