3.3.3 POST-OPERATIVE VISITS (DAYS 1 – 60)

All subjects implanted with a study lens will be seen for 1 Day, 1 Week, 1 and 3 Month assessments as outlined in Appendix A.

IN ADDITION, the second eye, fellow eye and enrolled in the study, will be implanted during this time period. It is recommended (at the final discretion of the Investigator), to complete this procedure as close to the 1 Week Visit (after first eye cataract extraction) as possible. Since second eye assessments will be completed on the same schedule as the first eye assessments (see Appendix A – Table 1), this will allow the subject further convenience in attending as many post-operative biometric assessment visits as possible.

The Investigator will carry out the second eye surgical procedure as specified in the Surgical Procedure Manual and the following details will be captured in both Source Documents and eCRFs:

- Date of surgery
- Operative eye
- Incision location and size
- Ophthalmic Viscoelastic Device (OVD) used
- Anesthetic used pre-, intra-, and post-operatively (ophthalmic and systemic)
- Model, serial number, and diopter of HMTIOL implant components
- Toric IOL power and axis orientation
- IOL injection device

Once the subject is confirmed stable post-surgery, provide post-operative instructions and discharge.

NOTE: A concomitant medication, AE, and SAE collection must be continued throughout the course of the study. Any outcomes resulting in unacceptable RRE (as determined between Investigator and Subject), can be addressed with spectacles, a contact lens, or surgical correction. Any PO surgical adjustments to address RRE (cornea refractive surgery, lens exchange, lens rotation, etc.) will be carried out as determined to be in the best interest of the subject. The course of treatment will follow the Investigator's SOC and be collected as a concomitant procedure. If surgical correction of the RRE is performed during the investigation period, the refractive error prior to secondary surgery is reported as the final result.

3.3.4 3 MONTH VISIT (DAY 80-100)

Assessments will be completed as indicated in Appendix A – Tables 1 and 2. In the event the second eye is out of window at this visit, the subject will return in-window to complete second eye assessments.

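### As visibly written, SAP 5.8.5 and 5.7 item 7 count a surgeon's rotation or exchange of the optic as lens behaviour, because no rule covers adjusted eyes

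*SAP*

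**What the plan says.** SAP 5.8.5 sets the rule: "The rotation of IOL meridian will be calculated for each eye from Day 0 to every postoperative visit". SAP 5.7 item 7 defines the endpoint as "Rotation of IOL meridian from the day of surgery to 3 months, and between all adjacent visits", with cut-offs at 5, 10, 20 and 30 degrees and the absolute value. SAP 5.8 summarises all effectiveness endpoints "based on the Implanted Eye Population", and SAP 7.1.2 defines that population by successful implantation alone. An eye adjusted later therefore stays in. Protocol 8.3.2.5 words the calculation in the same way and shows no exception.

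Protocol 3.3.3 foresees the event: "Any PO surgical adjustments to address RRE (cornea refractive surgery, lens exchange, lens rotation, etc.) will be carried out" as judged best for the subject. It then gives one rule for results after surgical correction: "the refractive error prior to secondary surgery is reported as the final result". That rule concerns refraction, and nothing visible extends it to the meridian.

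On counting, protocol 6.1.1 keeps optic exchange and rotation done to refine refraction out of AE reporting. SAP 5.4 leaves optic exchange and rotational adjustment out of the SSI rate. Protocol 4.8.2 does require the procedure to be captured as a concomitant procedure, with an indication.

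**The concern.** Rotational stability is a stated objective in protocol 2.0 and SAP section 1. The rotation endpoint should describe what the lens does by itself. This lens is built so that the optic can be turned or exchanged after surgery, so adjustment is a foreseeable event and not a protocol deviation.

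Once an optic has been turned, the angle between Day 0 and 3 months contains the surgeon's movement as well as any drift, and the two can cancel or add. The adjacent-visit interval that contains the procedure records the turn as rotation. After an exchange, the reference meridian and the later meridian belong to different optics.

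The protocol already avoids this problem for refraction by reporting the value before surgery. Rotation has no visible counterpart. No visible summary is required to count adjustments either, so a reader of the tables might not know that any 3-month value was affected.

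**Working it through.** There is no power or sample-size calculation to reproduce: the study is descriptive, and SAP section 6 states 17 eyes without deriving them. The check is to apply the stated rule to adjusted eyes and see what it returns.

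**Inputs.** 17 eyes (SAP 6). Cut-off of 5 degrees or less (SAP 5.7 item 7). Visit windows of Day 30-60 for 1 month and Day 80-100 for 3 months (protocol Appendix A). Weight of one eye: 1/17 = 5.9 percentage points.

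**Assumed data.** Sixteen eyes rotate 2 degrees each (sum 32). The seventeenth has no rotation except as stated.

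- **A: 20-degree drift seen at 1 month, then turned back.**
  - As written, 3 months: 17/17 = 100% within 5 degrees, mean 32/17 = 1.88 degrees.
  - By the last pre-procedure meridian: 16/17 = 94.1%, mean (32 + 20)/17 = 3.06 degrees. The difference is 20/17 = 1.18 degrees.
  - The 1-month row shows 16/17 under either rule. As written, the corrective turn also appears as 20 degrees of rotation between 1 and 3 months.
- **B: stable eye turned 15 degrees after the 1-month visit.**
  - As written, 3 months: 16/17 = 94.1%, mean (32 + 15)/17 = 2.76 degrees.
  - By the pre-procedure meridian: 17/17 = 100%, mean 32/17 = 1.88 degrees. The difference is 15/17 = 0.88 degrees.
- **C: 20-degree drift and its correction both between the 1-month and 3-month visits**, which can lie 80 - 60 = 20 to 100 - 30 = 70 days apart.
  - As written, every scheduled row reads 17/17.
  - By the last pre-procedure meridian: 16/17 if an unscheduled visit measured the drift, and still 17/17 if none did.

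A and B show that the error can run in either direction. Leaving the adjusted eye out would not cure A: the 3-month figure becomes 16/16 = 100%, because the eye that drifted is the one removed.

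**How likely is an adjusted eye?** The documents give no adjustment rate for this lens and no number of subjects. The rates below are assumptions; 6.7% is the repositioning figure that protocol 1.0 gives for another toric lens. The formula is P(at least one) = 1 - (1 - p)^m. Here m = 17 if eyes are independent, and m = 9 if eyes are fully correlated within subjects (8 bilateral subjects plus 1).

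| Assumed rate p | m = 9 | m = 17 |
|---|---|---|
| 2% | 1 - 0.98^9 = 17% | 1 - 0.98^17 = 29% |
| 6.7% | 1 - 0.933^9 = 46% | 1 - 0.933^17 = 69% |
| 10% | 1 - 0.90^9 = 61% | 1 - 0.90^17 = 83% |

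At 6.7%, the expected number of adjusted eyes is 17 x 0.067 = 1.14.

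**Does another provision deal with it?** The Per Protocol population (SAP 7.1.3) removes major deviations, and a permitted adjustment is not one. Rotation is also not among the outcomes named for that population.

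**The case against.** The strongest objection is redaction. SAP 5.8.5 has a redacted gap, as do SAP section 2 (Scope), SAP 5.1 and protocol 8.3.2.5, and two sections in the SAP contents list are blacked out. The gap in 5.8.5 sits where 5.8.4 describes signed rotation, so it may hold only that sentence, but a handling rule cannot be excluded. This stands: the point concerns the visible text only.

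Several stronger readings are tempting, and the documents do not support them:

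- **Drift would be hidden altogether.** Drift measured at an earlier visit stays in that visit's row. Protocol 3.3.5 provides for unscheduled visits, and SAP 5.8.5 refers to every postoperative visit, so a reading between scheduled visits is possible though not assured.
- **Adjustments go unrecorded.** Protocol 4.8.2 requires the procedure on its own eCRF, with an indication under ocular history or AE. The event behind an adjustment might also be reported as an AE or device deficiency. What is missing is a visible requirement to count the adjustments.
- **The SAP cancels the protocol's refraction rule.** SAP section 2 says that "analyses described here supersede those described in the Investigational Plan", but the rule in protocol 3.3.3 is a reporting instruction outside the protocol's statistical section, and nothing visible withdraws it.
- **The misalignment endpoint contradicts itself.** SAP 5.7 item 6 reads "IOL meridian misalignment on the day of surgery", while SAP 5.8.4 says "The final rotational meridian of the IOL will be compared to the planned position". Final can mean final at the end of surgery. This is an ambiguity, not a demonstrated error.

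It can also be said that carrying a pre-procedure value forward sits uneasily with the no-imputation rule in SAP 5.1. The value is measured, and the protocol treats refraction in the same way, but the SAP should state it as part of the endpoint definition.

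Finally, the results are descriptive and whether any eye was adjusted is not stated. Both limits stand.

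**Conclusion.** The point holds on the visible text. The stated rule covers every implanted eye and every visit. For an eye whose optic has been turned or exchanged, it returns an angle that mixes surgery with lens behaviour. This is more than missing detail, because an analyst who follows the rule exactly obtains a misleading 3-month value.

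One adjusted eye moves a threshold percentage by up to 5.9 points. In the examples it moves the mean absolute rotation by 0.9 to 1.2 degrees. The direction depends on whether the surgeon undid a drift or turned a stable lens. No error rate or power is affected.

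The conclusion rests on two conditions: that the redacted text holds no handling rule, and that at least one eye was adjusted. The documents settle neither. The probabilities above depend on assumed rates and do not show that any adjustment took place.

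**What to change.** First check the unredacted SAP. If it holds no rule, make these changes:

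1. **SAP 5.8.5 and 5.7 item 7.**
   - For an eye with surgical rotation, repositioning or exchange of the optic or IOL, take rotation from the last meridian measured before the procedure, at a scheduled or unscheduled visit. This matches the protocol 3.3.3 rule for refractive error.
   - Keep that eye in the Implanted-Eye denominator at 3 months, with a footnote. If it has no postoperative meridian before the procedure, report it as not available.
   - Do not count the adjacent-visit interval containing the procedure as lens rotation.
   - Show the as-measured result for all eyes as a labelled secondary row.
2. **Listing and count.** List each adjusted eye with its meridians before and after the procedure. Beside the SSI rate in SAP 5.4 and 5.5, report n (%) of implanted eyes with optic exchange or rotational adjustment. The AE and SSI definitions stay as they are. If no eye was adjusted, the row reads 0/17 and settles the question.

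Two side clarifications can be made at the same time: the time point meant in SAP 5.7 item 6 and 5.8.4, and whether the refraction rule of protocol 3.3.3 carries into the SAP.

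The cost is a few sentences, one extra row, one count and a short listing. No new data are needed: the procedures are already captured, and rotational stability is scheduled at surgery and at every postoperative visit (protocol Appendix A). There are two downsides. The carried value misses any drift after the last pre-procedure reading, as in example C without an unscheduled visit. The stability figures may also look less favourable.
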